
Study Design

Phase*

Not applicable

Design

a) prospective multicenter observational cohort study: phenotypes and patient characteristics will be compared among 4 psoriatic arthritis clinics in the United states

Study duration

The length of subject participation in the trial will be approximately 3 months. Estimated 2 years to enroll all subjects and complete study.

Resources necessary for human research protection

Describe research staff and justify that the staff are adequate in number and qualifications to conduct the research. Describe how you will ensure that all staff assisting with the research are adequately informed about the protocol and their research related duties. Please allow adequate time for the researchers to conduct and complete the research. Please confirm that there are adequate facilities for the research.

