Patients may be recruited before or after a new patient visit or return visit. In the case that the visit encounter is completed before enrollment, only the additional information not collected for clinical purposes will be collected. In other words, most of this information is collected in a routine clinic encounter. The information collected during that encounter will be used to complete as much of the CRF as possible and then the additional elements from the CRF will be completed by the research coordinator or site PI following that visit using information from the visit notes. After informed consent is obtained by a member of the study team listed on HS-ERA, a detailed history about the patient's arthritis will be taken and a complete examination will be performed by the rheumatologist. Patients will complete a set of Patient Reported Outcome (PRO) surveys electronically or on paper. Participants may also choose to have the survey link emailed and complete the PRO's within the 2 weeks following the baseline enrollment visit. Results of laboratory tests and radiography obtained for clinical purposes will be recorded. We will record the therapeutic regimen planned at the end of the clinical encounter. This data will be collected by the rheumatologist and the research coordinator at each site. Patients will also undergo a blood draw by venipuncture at the outpatient lab. Approximately 40 mL (4 tubes) of blood will be drawn at each visit. No more than 50 mL will be drawn at each visit. Clinical labs may also be drawn at this time. The study team will pick up the blood, process it, and store it onsite at UPenn/UPHS. The research blood draw will be ordered in EPIC and charged to the study but all other items in this study are considered clinical care and will be charged to insurers/subjects as usual. At a follow up visit approximately 3 months from the initial study visit, a thinned version of the CRF will be used to update the information collected from the participant and record any changes and response to therapy. . The participant will also fill out a different version of patient outcome measurements, have a complete examination performed by a rheumatologist, and undergo a blood draw again. A link to the PRO surveys will be emailed out 2 weeks prior to the scheduled follow-up visit and will be available until 2 weeks after the visit. Participants can also choose to complete the PROs at the visit on paper or electronically. The blood and information collected throughout this study will be used to build a repository for future research projects. The de-identified information stored in the redcap will available to the study teams at each of the sites involved in this study and to those PIs for future research. Researchers not involved in this study will not be permitted to request or use data or samples from this study. Blood samples will be processed and stored at individual sites. Blood samples may be shipped to a central location for further testing but will not be made available to outside researchers. Further testing will be focused on bio-markers of treatment response and disease progression. Participants may retract permission and ask that their samples be destroyed.

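### Emailed baseline PROs may be answered up to 2 weeks after the enrolment visit with no requirement that this precede the first TNFi dose, so some baseline PROs can be on-drug

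*Combined protocol and SAP*

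**What the plan says.** Under Study Procedures (Procedures), the general rule is that "Patients will complete a set of Patient Reported Outcome (PRO) surveys electronically or on paper". An emailed link is an additional choice, and those who take it may answer "within the 2 weeks following the baseline enrollment visit". Recruitment may follow the clinic visit: "In the case that the visit encounter is completed before enrollment, only the additional information not collected for clinical purposes will be collected". No maximum gap between visit and enrolment is given.

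On treatment, the same section says: "We will record the therapeutic regimen planned at the end of the clinical encounter". The follow-up form is to "update the information collected from the participant and record any changes and response to therapy". Neither item is stated to be the date of the first dose. Key inclusion criteria define entry by starting a TNFi, without placing that start relative to the baseline assessments.

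Follow-up is timed from the visit: "At a follow up visit approximately 3 months from the initial study visit". The follow-up PRO link "will be emailed out 2 weeks prior to the scheduled follow-up visit and will be available until 2 weeks after the visit", and the follow-up PROs are described as a different version from those at baseline. Study duration adds: "The length of subject participation in the trial will be approximately 3 months".

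The Analysis Plan covers between-centre comparisons only. It has no response analysis and no rule on PRO timing. Subject Confidentiality notes that the shared database holds date elements.

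**The concern.** Aim 1 (Primary outcome variable(s)) concerns response to therapy by several measures. Aim 2 (Secondary outcome variable(s)) concerns responsiveness, with the results meant to guide the choice of outcomes for later trials. Both rest on change from a baseline that ought to be untreated by the new drug. If part of the improvement has already happened when the baseline PRO is answered, the recorded change is too small.

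The emailed window applies to PROs and not to the examination. Any shift would therefore fall on one class of instrument, in a study whose second aim is to choose among instruments. It is also a consequence of following the stated procedure, not of departing from it.

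**Working it through.** **The plan's own figure.** The document gives no figure on this point. Its only computed result, 82% power for the comparison of four centres, concerns another question. It reproduces as 0.8225 (one-way ANOVA, 20 per group, means 0, 2.75, 2.75 and 5.5, SD 5, alpha 0.05) and plays no part below.

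**Inputs from the document (Procedures).** Emailed baseline PRO on day 0 to 14 after the visit; follow-up about 3 months from the visit; follow-up PRO from 14 days before to 14 days after that visit.

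**Assumptions, not in the document.** Three months is 91 days. Enrolment is on the visit day. L is the lag in days from visit to first dose. p is the share of patients who use the emailed link and start at lag L. Improvement is linear from the first dose. The instrument is used at both visits.

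**Step 1: one patient replying on day 14.** Days on drug at the baseline PRO = max(0, 14 − L). Share of change lost = (14 − L)/(91 − L), or zero once L reaches 14.

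| L (days) | Days on drug at baseline PRO | Share of change lost |
|---|---|---|
| 0 | 14 | 14/91 = 15.4% |
| 3 | 11 | 11/88 = 12.5% |
| 7 | 7 | 7/84 = 8.3% |
| 14 or more | 0 | 0% |

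The 15.4% is not an upper bound. At L = 0 it becomes 14/77 = 18.2% if the follow-up PRO is answered two weeks before the visit, and 14/105 = 13.3% if two weeks after.

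**Step 2: the cohort, replies spread evenly over days 0 to 14.** Mean days on drug = (14 − L)²/(2 × 14). Divide by (91 − L) for the mean share lost among emailed-link users, then multiply by p, here 0.25.

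| L (days) | Mean days on drug | Mean share lost, link users | Mean change lost, p = 0.25 |
|---|---|---|---|
| 0 | 98/14 = 7.0 | 7/91 = 7.7% | 1.9% |
| 3 | 60.5/14 = 4.3 | 4.3/88 = 4.9% | 1.2% |
| 7 | 24.5/14 = 1.75 | 1.75/84 = 2.1% | 0.5% |
| 14 or more | 0 | 0% | 0% |

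**Step 3: the unfavourable corner.** With L = 0 and every emailed reply on day 14, mean change lost = p × 15.4%: 1.5% at p = 0.10, 3.8% at p = 0.25 and 7.7% at p = 0.50.

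Faster early improvement would raise these figures. The document gives no time course, so that is not sized.

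**The case against.** The strongest reply is that the effect needs three things together: choosing the emailed link, replying late, and starting drug before replying. Email is an option beside paper and electronic completion, and the document gives neither uptake, reply times nor lag. What is recorded at baseline is a planned regimen, so there is no reason to treat same-day dosing as the typical case. This stands. It is why the cohort figures are shown across lags and the effect is called probably small. It does not remove the gap: the stated procedure permits on-drug baselines.

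The follow-up PROs are a different version and the instruments are not listed. This also stands, and it limits the point to instruments used at both visits.

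The CRF is not shown and the database holds dates, so the first-dose date may already be captured. A reader might infer that the study cannot identify post-dose forms; the document does not support that. Holding the date would still not supply a pre-dose instruction or a planned use for it.

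A reader might also infer that timing follow-up from the visit is an error, since weeks on drug then vary: at a 13-week visit, (91 − L)/7 gives 13.0, 11.0 and 9.0 weeks for lags of 0, 14 and 28 days. In a real-world study with visit-based follow-up this is a defensible design. Reporting weeks on drug is an analyst's option, not a correction.

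Finally, a strict pre-dose rule would leave no email window for a patient dosed on the visit day, and could not be met by one dosed before enrolment. That stands, and the fix allows for both.

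**Conclusion.** The point holds in a limited form. The stated baseline window can produce on-drug baseline PROs, and for instruments used at both visits this tends to understate change in Aims 1 and 2. Under the assumptions above, one patient replying on day 14 loses between 0% and about 15% of the change depending on lag (13% to 18% at zero lag across the follow-up PRO window). With a quarter of patients on the emailed route and evenly spread replies, the cohort mean loses about 2% or less. Lag and share are assumptions, so the real size is unknown and probably small.

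Two stronger conclusions are tempting and unsupported. One is that ACR20 is biased: the document does not list the ACR20 components or say which instruments supply them, and the blood tests that it mentions in Background are outside the PRO window. The other is that the MCII is biased: no method for estimating it is given. This is an inexpensive improvement, not a threat to the study.

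**What to change.** 1. In the Procedures section, add that baseline PROs are to be completed on or before the first TNFi dose where possible, within the existing 2-week window, and at the visit on paper or electronically if the first dose is due that day. The email option and visit schedule stay, and nothing about when drug is started changes.
2. Record the PRO completion date and the actual first-dose date, if the CRF does not already do so.
3. When the response analysis is written, keep all baseline forms in the main analysis; flag post-dose forms, including those from patients dosed before enrolment; report their number; and run a sensitivity analysis restricted to pre-dose forms.

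Items 1 and 2 can be made now; item 3 has to wait for a response analysis. Reporting weeks on drug at follow-up is optional.

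The cost is one sentence, at most two date fields and a little analysis. The downside is possibly a few missing or flagged baseline forms.
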